9 SUPPORTING DOCUMENTATION AND OPERATIONAL CONSIDERATIONS

9.1 REGULATORY, ETHICAL, AND STUDY OVERSIGHT CONSIDERATIONS

9.1.1 INFORMED CONSENT PROCESS

ADNI: We are requesting a waiver of written informed consent for all ADNI data for the following reasons: 1) The data is retrospective and will be downloaded from a database, 2) There is no additional data collection, and 3) It would be impractical to consent patients (due to large numbers) if written informed consent of patients were required. A data use agreement with ADNI will be completed prior to downloading the data for analysis from the ADNI database.

Clinic: All research study staff will maintain certification in human subject's protection. All study investigators and staff will take an active role in developing procedures to protect against or minimize potential risks to the safety and well-being of enrolled participants. Potential research subjects will be informed that participation in this study is voluntary and will not be discriminated against if they choose not to participate. Written informed or electronic consent and assent will be obtained from participants, and family member/caregivers or legally authorized representatives (LAR). Participants will be asked to describe in their own words the study's expectations. Subjects will be informed that they can withdraw from the study at any time and will be given a copy of the consent form. Subjects will have written assurance that while de-identified individual subject data may be available to other researchers for research purposes, or used to improve the software program, only a summary of the results will ever be published or otherwise publicly released. Subjects will be assured that participation in the study will be strictly confidential, that any identifying information will be available to the study staff only, and that no identifying information concerning the data and results will be made known.

Potential research subjects will be informed that participation in this study is voluntary and that their decision to participate will not reflect upon their relationships with the Center for Memory and Aging, Regions Hospital, or HealthPartners. Subjects will be informed that they can withdraw from the study at any time and will be given a copy of the consent form.

With the electronic consent via REDCap the patient/caregiver providing consent will be able to review the consent form themselves and sign electronically with a stylus, touch screen, or cursor using a signature field in REDCap. After the individual has received the link and can view the consent form, the research staff member will go through the consent form with the individual as would be typical in person. Following the consent conversation, the staff member will sign and e-mail the consent and HIPPA electronically to the patient. The patient will electronically sign, certify, and submit the consent and HIPPA in REDCap. A fully executed PDF copy of the consent and HIPPA will be provided electronically to the patient for their records as well as saved via the auto-archiver function in REDCap.

9.1.2 CONFIDENTIALITY AND PRIVACY

Participant confidentiality and privacy is strictly held in trust by the participating investigators, their staff, the safety and oversight monitor(s), and the sponsor(s). This confidentiality is extended to the data being collected as part of this study. Data that could be used to identify a specific study participant will be held

in strict confidence within the research team. No personally-identifiable information from the study will be released to any unauthorized third party without prior written approval of the sponsor/funding agency.

All research activities will be conducted in as private a setting as possible.

All study regulatory binders will be stored in a locked file cabinet within a secure office. The internal study monitor, representatives of the IRB, or regulatory agencies, may inspect all documents and records required to be maintained by the investigator, for the participants in this study. The clinical study site will permit access to such records.

The study participant's contact information will be securely stored at the clinical site for internal use during the study. At the end of the study, all records will continue to be kept in a secure location for as long a period as dictated by the reviewing IRB, Institutional policies, or sponsor/funding agency requirements.

A unique study ID code unrelated to the medical record number or other study subject-specific information will be assigned to each patient and used to link data from various sources and needed for analysis. The study number will be used on the RedCap database and Infinitome Program. All imaging data uploaded from the NSC research site will be de-identified and uploaded to the Infinitome cloud-based server.

Infinitome program uses an industrial grade cyber security that is superior to what is offered at the leading medical device companies. No personal health information is stored on servers and only de-identified scans are stored on a dedicated edge node on encrypted MinIO instances. Patient data is only accessed through authenticated calls from Kubernetes pods contained in the VPC. The web service requires user authentication. Only the data related to a specific facility can be retrieved through authenticated calls and are restricted to their use

The PI will ensure all mechanisms used to share data will include proper plans and safeguards for the protection of privacy, confidentiality, and security for data dissemination and reuse (e.g., all data will be thoroughly de-identified and will not be traceable to a specific study participant). Plans for archiving and long-term preservation of the data will be implemented, as appropriate.

9.1.4 SAFETY OVERSIGHT

There is no Data Safety Monitoring Board for this study, as there is no intervention and has minimal risks

9.1.5 CLINICAL MONITORING

N/A, refer to next section.

9.1.6 QUALITY ASSURANCE AND QUALITY CONTROL

Study staff will perform internal quality management of study conduct, data collection, documentation and completion.

Quality control (QC) procedures will be implemented as follows:

Informed consent --- Study staff will review both the documentation of the consenting process and 10% of the completed consent documents. Feedback will be provided to study staff to ensure proper consenting procedures are followed.

Protocol Deviations – The study team will review documented protocol deviations on an ongoing basis and will implement corrective actions when the quantity or nature of deviations are deemed to be at a level of concern.

Should independent monitoring become necessary, the PI will provide direct access to all study related sites, source data/documents, and reports for the purpose of monitoring and auditing by the sponsor/funding agency, and inspection by local and regulatory authorities.

9.1.7 DATA HANDLING AND RECORD KEEPING

9.1.7.1 DATA COLLECTION AND MANAGEMENT RESPONSIBILITIES

Data collection will be the responsibility of the research study staff under the supervision of the PI. The PI will be responsible for ensuring the accuracy, completeness, legibility, and timeliness of the data reported.

Data collection/reporting tools will be developed internally (i.e. CRFs or eCRFs (RedCap Database) and source documents). Data collected and stored electronically will remain confidential and secure (e.g. secured server, encrypted data, password protected file).

9.1.7.2 STUDY RECORDS RETENTION

Investigator records will be retained in accordance with regulatory, organizational and sponsor or grantor requirements. All records will be maintained securely with limited access. Disposal of investigator records will be done in such a manner that no identifying information can be linked to research data.

9.1.8 PROTOCOL DEVIATIONS

This protocol defines a protocol deviation as any noncompliance with the study protocol. The noncompliance may be either on the part of the participant, the investigator, or the study site staff. As a result of deviations, corrective actions will be developed by the site and implemented promptly.

9.1.9 PUBLICATION AND DATA SHARING POLICY

This study will be registered at ClinicalTrials.gov, and results information from this study will be submitted to ClinicalTrials.gov. In addition, every attempt will be made to publish results in peer-reviewed journals.

Data from the de-identified images may be utilized by Omniscent for improvement of Infinitome program and potential future imaging research studies.

9.1.10 CONFLICT OF INTEREST POLICY

The study leadership in conjunction with HealthPartners Institute has established policies and procedures for all study group members to disclose all conflicts of interest and will establish a mechanism for the management of all reported dualities of interest.

9.2 ADDITIONAL CONSIDERATIONS

N/A

11 APPENDIX

11.1 SCHEDULE OF VISITS

Procedure	Screen/Consent	Cognitive	Imaging	Results Review
	Visit 1	Visit 2	Visit 3 (Within 3 weeks of visit 2)	Optional (After Visit 3)
	Telephone/Video	At NSC	At NSC	At NSC or Virtual
E-consent	X			
Medical History	X			
Demographics	X			
MRI Contraindications	X		X	
Inclusion/Exclusion Criteria	X	X	X	
MMSE	X			
Cognitive Tests		X		
MRI Imaging			X	
Brain Imaging Results				X

Updated *A Priori* SAP

06 FEB 2024

Aim 1

Our primary aim was to evaluate the role of rs-fMRI and connectomic analysis as a diagnostic imaging biomarker of disease for LSBN deterioration in DLB by comparing a clinical population of DLB patients with the ADNI 2/3 cohort of CN and AD/CI subjects. Specifically, we compared FC scores of prespecified parcellation pairs between the three groups using a one-way ANOVA. Eight parcellation pairs were chosen as the primary pairs, and twenty-two as the exploratory pairs.

Aim 2

Our secondary aim (aim 2) was to correlate cross-sectional dysfunction between LSBN parcellations with specific neuropsychological abnormalities in DLB patients. To accomplish this, we performed a two-stage analysis. First, we compared cognitive test scores between groups to understand which successfully distinguished between the cohorts. When possible, test scores were normed, i.e., converted to a Z- or T-score adjusted for age, sex, and years of education.

Primary Comparisons/A Priori Hypotheses:

- 1) *ADAS Number Cancellation Targets will be lower in DLB patients*
- 2) *Trails B time will be higher in DLB patients*
- 3) *Clock Drawing Tests will be lower in DLB patients*
- 4) *ADAS construction praxis score will be lower in DLB patients*
- 5) *Category Fluency Animals will be lower in AD patients*
- 6) *RAVLT recognition will be lower in AD patients*

The remaining comparisons were exploratory: Trails A time, RAVLT immediate recall, RAVLT delayed recall, Functional Activities Questionnaire (FAQ), Logical Memory Immediate, and Logical Memory Delayed. Digit Span Forward, Digit Span Backward, and Boston Naming Test were either missing or highly incomplete in ADNI controls; therefore, they were described in the DLB cohort only.

In the second part of the Aim 2 analysis, we correlated test scores with FC scores from the primary parcellation group in Aim 1, within diagnosis (DLB, CN, or AD/CI) and compared these correlations across diagnosis group. As above, we prespecified 4 hypotheses to test and consider the remaining correlations to be exploratory. Because of the high volume of statistical tests performed in the exploratory analysis, we used the Holm correction to adjust the p-values in the exploratory correlations only.

Primary/ A Priori Hypotheses:

- 1) *Caudate R / Substantia Nigra R and the Clock Drawing Test will be differently correlated for DLB patients vs other groups.*
- 2) *Caudate R/ Substantia Nigra R and the ADAS Number Cancellation Targets will be differently correlated for DLB patients vs other groups.*
- 3) *FST R/PH R and the ADAS construction praxis will be differently correlated for DLB patients vs other groups.*
- 4) *FST R / PH R and the Clock Drawing Test will be differently correlated for DLB patients vs other groups.*

With respect to the exploratory correlations, we used a significance threshold of $p < 0.15$, which is an accepted approach for detecting effects in emerging research areas where it's preferable to err on the side of identifying novel effects versus failing to reject a null hypothesis when it is false (Type II error).

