1 PROTOCOL SUMMARY

1.1 SYNOPSIS

Title:	Connectomic Analysis in Dementia with Lewy Bodies: A Potential Diagnostic Imaging Biomarker
IRB Number:	A#_21-037_____
Study Description:	This is a cross-sectional study in patients with Lewy Body Dementia (DLB) with two comparison groups (AD and cognitively normal controls) drawn from a publicly available database called ADNI-2/3. We intend to study dysfunctional large scale brain networks (LSBNs) in DLB by comparing resting state functional MRI (rs-fMRI) imaging data. We propose using a novel cloud-based automated imaging software processing program that identifies abnormal brain networks or connectomes using rs-fMRI and data from the Human Connectome Project (HCP).
Specific Aims:	Specific Aim #1: Evaluate the role of rs-fMRI and connectomic analysis as a diagnostic imaging biomarker for LSBN deterioration in DLB by comparing a clinic population of DLB patients with pre-existing data from an ADNI 2/3 cohort of CN and MCI/mild AD subjects Specific Aim #2: Correlate cross-sectional dysfunction between LSBN parcellations with specific neuropsychological abnormalities in DLB patients
Outcomes:	Aim 1 Outcomes: Functional connectivity (FC) scores between pairs of LSBN parcellations. Aim 2 Outcomes: Functional connectivity (FC) scores between pairs of LSBN parcellations vs Neuropsychological test scores
Study Population:	Inclusions: 1) Age 40- 90 years, 2) Established DLB diagnosis (McKeith Criteria 2017), 3) MMSE>15 Exclusions: 1) Other forms of dementia including, but not limited to Alzheimer's dementia, frontotemporal dementia, vascular dementia, NPH, etc, 2) Inability to tolerate brain fMRI, 3) Risk of brain fMRI due to implants or metal. Sample Size: We plan to enroll 19 DLB patients. 38 AD and 38 CN age and sex-matched subjects will be selected from the ADNI-2/3 database.
Description of Sites/Facilities Enrolling Participants:	Participants will be enrolled at HealthPartners Neuroscience Center, located at [name].
Study Duration:	The duration of this study is 1.5 years.
Participant Duration:	Participants should take about 3 hours - total time for all the visits, that may be conducted within 6 weeks

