3 OBJECTIVES AND ENDPOINTS

Aim 1: Evaluate the role of rs-fMRI and connectomic analysis as a biomarker of disease in DLB using data from an ADNI-2/3 population of MCI and mild AD subjects and a clinic population of DLB subjects

Functional connectivity (FC) scores between pairs of LSBN parcellations

- Primary pairs of interest (see background for justification of these choices):
 - Locus coeruleus v. Basal nucleus of Meynert
 - Locus coeruleus v. Intralaminar nucleus of thalamus
 - Basal nucleus of Meynert v. Intralaminar nucleus of thalamus
 - PH v. FST
 - Substantia nigra v. Caudate nucleus
- Exploratory pairs: Other 15 combinations of the pre-specified parcellations, other pairs of parcellations found to be anomalies by Infinitome program

Aim 2: Correlate cross-sectional and longitudinal dysfunction between LSBN parcellations with specific neuropsychological abnormalities in DLB Patients

Functional connectivity (FC) scores between pairs of LSBN parcellations (same primary pairs of interest as Aim 1).

Scores on neuropsychological tests: WMS-R Logical Memory Story A, Boston Naming Test Short, Category Fluency, WMS-R Digit Span Forward and Backward, ANART, RAVLT, Trails A/B, WMS-R Digit Symbol, Clock Drawing, NPI-Q, FAQ, ADAS-Cog 13

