4 STUDY DESIGN

4.1 OVERALL DESIGN

This is a cross-sectional study in patients with DLB with two comparison groups. The study includes analyzing resting state-functional MRI (rs-fMRI) imaging data in CN and AD subjects from the ADNI 2/3 database and in DLB subjects recruited from a multidisciplinary dementia clinic

Specific Aim #1: Evaluate the role of rs-fMRI and connectomic analysis as a diagnostic imaging biomarker for LSBN deterioration in DLB by comparing a clinic population of DLB patients with pre-existing data from an ADNI 2/3 cohort of CN and mild AD subjects

Specific Aim #2: Correlate cross-sectional dysfunction between LSBN parcellations with specific neuropsychological abnormalities in DLB patients .

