5 STUDY POPULATION

For ADNI 2/3 data, we will include CN and AD subjects who have undergone rs-fMRI images (with DTI and T1 images) and have cognitive/function testing data available. Below we describe the study population regarding clinic recruitment.

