5.5 STRATEGIES FOR RECRUITMENT AND RETENTION

Recruitment: For Alzheimer's Disease Neuroimaging Initiative (ADNI), analysis will be based on data available from the database. As such there are no recruitment or retention activities. rs-fMRI data as well as variables listed in Table 3 & 4 will be downloaded from ADNI-2/3 for age/sex-matched mild AD (with supportive biomarkers) and age/sex-matched CN patients.

Clinic Population: Potential DLB subjects will be referred to the study coordinator by clinicians in the neurology departments of HealthPartners and Park Nicollet. Participants with clinic visits will meet with research staff. Other patients will be mailed/e-mailed a letter and flyer/brochure. An informed consent form will be provided to those individuals expressing interest in the study. A video or phone encounter will be arranged to provide additional details of the study and informed consent. This study will be listed as one of the regional DLB investigations on the Alzheimer's Association Trial Match website. All referrals will be directed to study staff who will contact interested participants by phone. Participation will include one virtual visit and two in-person visits at HealthPartners Neuroscience Center.

To reach our target enrollment, we anticipate that we will need to screen 40 people, of those 19 individuals will sign the informed consent.

Remuneration: Participants will be provided gift cards totaling \$100 per subject for completing certain visits of the research study. The gift cards will be provided at the end of the study for completing the cognitive and imaging visits.

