7.2 ADNI DATABASE

A data use agreement with ADNI will be completed prior to downloading the data for analysis from the ADNI database (ADNI Database). A user login – for research staff will be used for downloading the data.

All necessary ADNI data for MCI, mild AD patients, and cognitively normal (CN) will be downloaded to a local secure server for further analysis.

Data will be obtained regarding demographics, medical history, cognitive assessments (as mentioned in earlier sections), MMSE for eligibility, biomarkers and imaging (as mentioned in the previous section). The imaging data will be uploaded and processed with the Infinitome software as stated in the previous sections.

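### The documents conflict on whether MCI/CI subjects belong to the 38-person Alzheimer comparator; if they do, the DLB contrast could mix disease type with stage

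*Combined protocol and SAP*

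**What the plan says.** **Places that include MCI.** The synopsis states Specific Aim 1 with "pre-existing data from an ADNI 2/3 cohort of CN and MCI/mild AD subjects". Section 3 words the same aim as "using data from an ADNI-2/3 population of MCI and mild AD subjects", and the Table 4 title for Aim 1 repeats this. Section 7.2 adds: "All necessary ADNI data for MCI, mild AD patients, and cognitively normal (CN) will be downloaded".

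**Places that name only AD or mild AD.** The synopsis sample size reads "38 AD and 38 CN age and sex-matched subjects will be selected from the ADNI-2/3 database". Section 4.1 has "pre-existing data from an ADNI 2/3 cohort of CN and mild AD subjects". Section 5 says "we will include CN and AD subjects who have undergone rs-fMRI images". Section 5.5 is the most specific: data are downloaded "for age/sex-matched mild AD (with supportive biomarkers) and age/sex-matched CN patients". The Table 4 group variable has the levels DLB, AD and CN, and section 8.2 powers the study on 38 AD.

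**The SAP.** The Updated A Priori SAP of 06 FEB 2024 compares DLB "with the ADNI 2/3 cohort of CN and AD/CI subjects". In Aim 2 it treats AD/CI as one diagnosis level beside DLB and CN. It does not define CI.

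**Related text.** Table 1 makes dementia essential to a DLB diagnosis, and section 5.1 enrols DLB at MMSE above 15. Section 7.2 lists MMSE for eligibility and biomarkers among the ADNI data, but gives no ADNI threshold. Section 8.1 uses a multivariate linear model with group as the factor; the SAP uses a one-way ANOVA on the three groups.

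**The concern.** DLB patients must have dementia. People with MCI need not. If the 38 comparators include CI subjects, a connectivity difference between DLB and AD/CI could reflect the disease, the stage, or both. Matching on age and sex does not deal with this, and a model whose only term is group cannot separate the two.

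Two analysts could build different comparator groups from the same text and both would comply. A reader of the results could not tell whether they concern DLB against AD dementia or DLB against a group of mixed stage. That matters for a study meant to evaluate a diagnostic imaging biomarker.

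**Working it through.** **1. What the text settles.** The synopsis includes MCI in its aim and omits it from its sample size. Table 4 includes MCI in its Aim 1 title and omits it from its group variable. The conflict therefore lies inside the current protocol and is not just a later SAP replacing older wording. AD, mild AD, and mild AD with supportive biomarkers can be read as one definition at different levels of detail. What cannot be reconciled is whether MCI is in or out. No section says how many of the 38, if any, are MCI or CI.

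**2. The plan's own power figure.** Inputs from section 8.2: 19 DLB, 38 AD, difference 0.05, SD 0.05, two-sided alpha 0.01.
- Standard error = 0.05 × √(1/19 + 1/38) = 0.01405.
- Noncentrality = 0.05 / 0.01405 = 3.559, on 19 + 38 − 2 = 55 df, critical t = 2.668.
- Noncentral-t power = 80.9%. The stated 81% reproduces.

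**3. How CI subjects would act.** Let m of the 38 be CI, with mean connectivity shifted by s from the AD mean. The comparator mean moves by (m/38) × s. The documents give neither m nor s, nor the sign of s.

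**4. Illustration with assumed m and s.** Simulated trials, equal-variance t-test at 0.01, other inputs as in step 2:

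| m of 38 | s | Shift in comparator mean | False positives, DLB = AD | Power for 0.05, shift opposing | Rejection rate for 0.05, shift adding |
|---|---|---|---|---|---|
| 0 | – | 0 | 1.0% | 81% | 81% |
| 5 | 0.0125 | 0.0016 | 1.0% | 77% | 84% |
| 10 | 0.0125 | 0.0033 | 1.2% | 74% | 86% |
| 10 | 0.025 | 0.0066 | 1.6% | 65% | 90% |
| 19 | 0.0125 | 0.0063 | 1.6% | 67% | 90% |
| 19 | 0.025 | 0.0125 | 3.9% | 48% | 95% |

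The results follow the assumptions. A shift of 0.05 in half the group, as large as the whole target difference, would give a false-positive rate of roughly 16–20%. The table shows the mechanism and is not an estimate for this study. The alpha of 0.01 comes from section 8.2; the SAP names eight primary pairs and states no alpha for Aim 1.

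**5. Cost of an AD-only contrast.** Same formula as step 2, with CI subjects removed and not replaced:

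| AD subjects | Power for 0.05 | Difference detectable with 80% power |
|---|---|---|
| 38 | 81% | 0.0495 |
| 28 | 75% | 0.0527 |
| 19 | 64% | 0.0581 |

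**The case against.** **MCI may never enter the group.** Most of the sections that govern selection, grouping and sample size name only AD. MCI appears in aim wording and a download list, and AD/CI could be shorthand for cognitive impairment due to AD. This stands as far as it goes: a reader might infer that CI subjects are among the 38, and no passage says so. But nothing rules it out, and the SAP's own label raises the question.

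**A severity gap would be visible.** A reader might infer that nothing in the plan would reveal a stage difference. That is too strong. Section 8.1 compares baseline characteristics across groups, Table 4 lists baseline cognition among the descriptors, and the SAP compares cognitive scores and the FAQ. These could show an overall gap between DLB and the comparator. They do not split AD from CI within the 38, and they do not separate stage from disease type in the connectivity contrast.

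**Other readings that go too far.**
- Counting every label as a separate conflicting definition. Several are compatible; the real conflict is MCI in or out.
- Calling DLB versus AD the main contrast. Aim 1 is a three-group comparison, and section 8.2 does not rank the pairs.
- Saying that Aim 2 hypotheses 5 and 6 have no identifiable group. With three groups in the SAP, their reference to AD patients most naturally means AD/CI; what is missing is that group's definition.

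**Dropping CI does not align stage.** This stands. DLB enrols at MMSE above 15, section 5.5 specifies mild AD, and no ADNI threshold is given.

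**Conclusion.** The inconsistency is certain and its consequence is conditional. The current text both includes and excludes MCI, and the SAP analyses an undefined AD/CI level. If CI subjects are present, the DLB versus AD/CI contrast could be biased either way, by an amount that cannot be computed from the documents. With a small CI share the effect is slight: in the illustration, 5 of 38 shifted by 0.0125 leaves false positives at about 1.0% and power at 77% when the shift opposes the true difference. Larger effects need larger assumed shares or shifts, and the documents support no particular values.

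This is a point that should be corrected. It is not a demonstration that the comparison is confounded. The 81% power in section 8.2 is arithmetically right for 19 against 38 at its stated inputs.

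**What to change.** 1. Define the comparator once (diagnostic categories, biomarker requirement, severity range), define CI, and use that definition in every section and in the SAP.
2. Report how many of the 38 are AD and how many CI, with MMSE for each.
3. If CI subjects are present, add a contrast of DLB against AD only, using section 5.5's wording of mild AD with supportive biomarkers. Make it primary only if results have not been seen. The SAP is written in the past tense; if results are known, label it a post hoc sensitivity analysis beside the pooled result.
4. State that this contrast removes the mixed-group problem but does not by itself equalise severity.
5. If CI subjects are removed and not replaced, restate the DLB–AD power.

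The cost is SAP wording, one small table and one extra contrast on data already held or planned for download. The downside is precision: the power loss in the last table above, unless more ADNI scans are selected and processed.

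Optionally, and not as a remedy for stage, adjust connectivity for age, sex and education. All three are already collected and education is not matched. This is a precision and balance step whose gain is unknown.

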7 STUDY ASSESSMENTS AND PROCEDURES

7.1 STUDY ASSESSMENTS FOR ENROLLED PATIENTS

7.1.1 DEMOGRAPHICS AND MEDICAL HISTORY

Demographic information will be collected, including: gender, age, race, ethnicity, height, weight, BMI, education, dementia diagnosis, co-morbidities (such as Diabetes, Hypertension) and e-mail address for consent.

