8 STATISTICAL CONSIDERATIONS

8.1 STATISTICAL ANALYSIS PLAN

Preliminary data analysis: One-way ANOVA will be used to compare demographic and baseline clinical characteristics across groups. **no missing data expected, SAS, p-value

Aim 1 Analysis: For the between-group analysis of functional connectivity, general linear model multivariate analysis of variance will be used with FC values between pairs of LSBN parcellations as dependent variables and group (DLB, AD, and CN) as a factor variable. Bonferroni post hoc test will be used to correct for multiple comparisons. The primary pairs of interest (see **Table 4**) based on available literature (see background and **Table 2**) will be analyzed first. Other combinations of these seven parcellations will be analyzed secondarily. If additional, unexpected anomalies are present between groups, we will test them in an exploratory fashion to advance this novel field of study.

Aim 2 Analysis: Pearson correlation analyses will be performed between functional connectivity values and neuropsychological test scores to evaluate the relationship between connectivity strengths and the clinical phenotype of DLB. Similar to Aim 1, we will focus on pre-specified pairs of interest, but will explore others if they present themselves in the functional connectivity analysis.

Table 4: Data Variables
Population Descriptors: age, sex, race, ethnicity, education, measures of baseline cognition (e.g. MoCA)
Aim 1: Evaluate the role of rs-fMRI and connectomic analysis as a biomarker of disease in DLB using data from an ADNI-2/3 population of MCI and mild AD subjects and a clinic population of DLB subjects
Group variable: DLB, AD, or CN

Dependent variables: Functional connectivity (FC) scores between pairs of LSBN parcellations
 
 • Primary pairs of interest (see background for justification of these choices): 
 ○ Locus coeruleus v. Basal nucleus of Meynert ○ Locus coeruleus v. Intralaminar nucleus of thalamus ○ Basal nucleus of Meynert v. Intralaminar nucleus of thalamus ○ PH v. FST ○ Substantia nigra v. Caudate nucleus • Exploratory pairs: Other 15 combinations of the pre-specified parcellations, other pairs of parcellations found to be anomalies by Infinitome program
Aim 2: Correlate cross-sectional dysfunction between LSBN parcellations with specific neuropsychological abnormalities in DLB Patients

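### Aim 1 matches comparators on age and sex but tests connectivity on group alone, which makes the test conservative and leaves education unadjusted

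*Combined protocol and SAP*

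**What the plan says.** **Selection of comparators.** The Synopsis (1.1) says "38 AD and 38 CN age and sex-matched subjects will be selected from the ADNI-2/3 database". Section 5.5 repeats the two matching variables: "age/sex-matched mild AD (with supportive biomarkers) and age/sex-matched CN patients". Education is not among them.

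**Aim 1 model.** Section 8.1 plans a multivariate general linear model "with FC values between pairs of LSBN parcellations as dependent variables and group (DLB, AD, and CN) as a factor variable". The Updated A Priori SAP of 06 FEB 2024 replaces this with a simpler test: "Specifically, we compared FC scores of prespecified parcellation pairs between the three groups using a one-way ANOVA". Neither text names a covariate, a term for the matched sets, or an adjusted sensitivity analysis.

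**Covariates available.** Section 7.1.1 states: "Demographic information will be collected, including: gender, age, race, ethnicity, height, weight, BMI, education". Table 4 lists "age, sex, race, ethnicity, education, measures of baseline cognition (e.g. MoCA") as population descriptors only. Section 8.1 adds that "One-way ANOVA will be used to compare demographic and baseline clinical characteristics across groups", but attaches no consequence for the Aim 1 model if an imbalance is found.

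**Aim 2, for contrast.** The 2024 SAP standardises the cognitive scores, where it can, for age, sex and schooling. It gives no reason for leaving these variables out of the FC comparison.

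**The concern.** Matching on age and sex equalises the groups on those variables. It does not remove the variation that age and sex produce within each group. A group-only ANOVA leaves that variation in its error term, so the standard error of each contrast is larger than the matched design warrants. With 19 DLB patients, precision is worth keeping.

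Education raises a different issue. DLB patients come from local clinics and comparators from a research database, so equal education cannot be assumed. A gap would enter the DLB contrasts if education also relates to FC.

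The 2024 SAP neither repeats nor withdraws the matching, and it calls the dementia comparator AD/CI. If matching was imperfect or was dropped, age and sex would become confounders too.

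**Working it through.** **Inputs from section 8.2:** 19 DLB, 38 AD and 38 CN (total 95); alpha 0.01; within-group SD 0.05; SD of group means 0.02; pairwise difference 0.05. **Assumed, because the documents give no figure:** R² of the covariates for FC, the education gap between groups, and the education-FC correlation.

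**1. The plan's own figures.**
- Pairwise: noncentrality = 0.05 / (0.05 × √(1/19 + 1/38)) = 1 / 0.281 = 3.56. The noncentral t with 55 df gives 80.9% (stated: 81%).
- F-test: λ = 95 × (0.02/0.05)² = 15.2. The noncentral F with df 2 and 92 gives 82.0% (stated: 80%). An SD of means near 0.0196, which rounds to 0.02, gives 80%.

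The stated power therefore reproduces for an unadjusted, unmatched comparison.

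**2. ANCOVA on group, age, sex and education.** The residual SD is 0.05 × √(1 − R²), so λ = 15.2 / (1 − R²). Three covariates leave 89 error df for F and 52 for the pairwise t.

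| R² | F-test power | Pairwise power |
|---|---|---|
| 0 | 81.9% | 80.8% |
| 2% | 82.9% | 81.7% |
| 5% | 84.4% | 83.1% |
| 10% | 86.7% | 85.4% |
| 20% | 91.2% | 89.9% |
| 30% | 94.9% | 93.8% |

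These figures ignore variance inflation from covariate imbalance.

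**3. Matched groups, analysed without adjustment.** The fair baseline is the design actually planned. Exact 1:2:2 matching was simulated: each DLB patient shares the matching-variable value with two AD and two CN subjects, and the group-only ANOVA is run at nominal 1%. Power is for a DLB-only shift of 0.05 (1 SD), which also gives λ = 15.2. Ranges cover two independent runs. The ANCOVA column takes the same R², so education is credited with no extra variance explained.

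| R² | Actual type I error | Unadjusted power | ANCOVA power | Gain, points |
|---|---|---|---|---|
| 10% | 0.64-0.65% | 82.9-83.0% | 86.7% | about 4 |
| 20% | 0.33-0.37% | 83.5-83.8% | 91.2% | 7-8 |
| 30% | 0.18-0.20% | 85.0-85.5% | 94.9% | 9-10 |

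At R² of 2-5% the ANCOVA figures of 82.9% and 84.4% stand only 1-2 points above the unadjusted test.

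**4. Education.** Shift in SD units = gap (SD) × within-group education-FC correlation. Noncentrality under no true difference = shift / 0.281, applied to the 19 v 38 t-test at 1%.
- Gap 0.5, correlation 0.1: shift 0.05 SD (0.0025 in FC units, 5% of the planned 0.05); error 1.1%.
- Gap 0.3, correlation 0.3: shift 0.09 SD; error 1.4%.
- Gap 0.5, correlation 0.5: shift 0.25 SD (0.0125 in FC units, 25% of the planned difference); error 4.4%.

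**The case against.** The omission is plain in the text; its size is not. Several counter-arguments deserve weight.

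- **No false positives from age and sex.** A reader might infer that a group-only model after matching inflates error. It does the opposite: as far as matching succeeds, the contrast is unbiased and the test is conservative. This stands.
- **Size of the gain.** Setting 82% against 95% suggests 13 points. That baseline ignores the matching; against the matched but unadjusted test the gain is at most about 10 points, and 1-2 at low R². This stands. The 40-90 age range in section 5.1 is an eligibility window and does not show the spread in the sample.
- **Education.** The bias needs both a gap and a correlation, and the documents give neither. With a correlation of 0.1 it is negligible. This stands, so the point has to remain conditional.
- **The Aim 2 precedent.** Standardising cognitive scores does not prove that FC needs the same adjustment. True, but it shows that the plan regards these variables as relevant, and no reason is given for omitting them from Aim 1.
- **Timing.** The 2024 SAP is in the past tense and reports that some tests were missing or largely incomplete in the ADNI controls, so comparator data had at least been inspected. Replacing the primary model at that stage could be a post hoc change. This stands and shapes the fix.
- **Alpha.** The 0.01 level comes from section 8.2, written for five primary pairs. The 2024 SAP has eight and states no Aim 1 alpha. The figures above therefore illustrate the protocol's level.
- **Scanner and site.** DLB scans come from one local scanner and comparators from ADNI. Covariate adjustment leaves that difference intact. This limits what the fix achieves but is no reason to leave known covariates out.

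**Conclusion.** The point holds as a precision recommendation with a conditional bias component, and should be acted on. It is certain from the text that comparators are matched on age and sex only, that the Aim 1 model contains group alone, and that no adjusted analysis is planned.

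The size rests on assumption. With the matching variables explaining 10-30% of FC variance, the nominal 1% F-test runs at roughly 0.6% down to 0.2% and gives up about 4 to 10 points of power; with 2-5% explained, 1-2 points. Education bias ranges from negligible (1.1% error) to noticeable (4.4%) over the assumed shifts, and is absent if education is balanced or unrelated to FC.

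The documents do not support reading this as an error in the power calculation, since the stated figures reproduce, or as evidence that the DLB contrasts are in fact confounded. If the matching was imperfect or abandoned, age and sex would join education as possible confounders and the case for adjustment would be stronger.

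**What to change.** Add to the Aim 1 analysis an ANCOVA for each FC pair, with group, age (continuous), sex and years of education. Report the adjusted DLB-AD and DLB-CN differences with 95% confidence intervals beside the unadjusted ANOVA. State in the SAP whether the final comparators were matched.

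Make the ANCOVA the primary model only if FC has not yet been compared between groups. Otherwise present it as an added adjusted analysis, labelled with its date.

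No new data are needed: sections 7.1.1, 5.5 (with Table 4) and 7.2 already provide for these variables. The statistical cost is 3 error df (92 to 89), about 0.2 points of power at most even if the covariates explain nothing (pairwise 80.9% to 80.8%; F-test 82.0% to 81.9%). The report should say that this adjustment does not address scanner or site differences between local and ADNI scans.
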